2.1.1 Inclusion criteria

- Patients 3 to 8 years following implantation of a CyPass-Stent between 2009 and 2014
- Willingness of patients to participate in the study and signing the written informed consent

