2.2 Study population

- We plan to examine at least 84 eyes. Therefore, we invite patients with at least 130 study eyes (see sample size calculation 2.7).
- All patients after implantation of a CyPass microstent on at least one eye. Excluded are patients which had combined operation (phacoemulsification with intraocular lens implantation and CyPass stent implantation)
- We will not invite the patients of whom we already have the long-term data available because they had been examined in the past at the department of Ophthalmology. We will take the available data from the medical records.
- Patients with secondary surgery due to CyPass failure will not be invited for the examination. We will collect the available data up to the date of the new operation from the patient's records and classify these cases as failure.

Protocol Version II 5-year CyPass results

- The following inclusion and exclusion criteria are considered for the prospective part of the study:

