2.3 Study design

Monocentric study with two parts:

- Retrospective part: Collection of preoperative, intraoperative and postoperative data from the medical records
- Prospective part: Inviting patients according to inclusion and exclusion criteria for a single examination and collection of postoperative data after an average of five years

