2.4 Study investigation plan

The pre- and intraoperative data, the data of the routine follow-up after 3 and 6 months postoperatively, as well as data of unscheduled examinations are taken retrospectively from the patient files.

- Collection of preoperative findings from the medical record:
 - i. Patient name, date of birth, gender, operated eye and surgery date
 - ii. General diseases and medications
 - iii. Eye diseases and already performed eye operations, if any
 - iv. Best corrected visual acuity
 - v. Topical and systemic glaucoma therapy and duration of glaucoma therapy
 - vi. Time of diagnosis of glaucoma, if available
 - vii. Intraocular pressure using Goldmann tonometer and time of measurement
 - viii. Central corneal thickness and pachymetric correction factor measured with the ultrasonic pachymeter or with Visante-OCT.
 - ix. Classification of the chamber angle width according to Shaffer classification
 - x. The lens condition or existing opacities of the natural lens or presence of an implanted intraocular lens at the time of surgery
 - xi. Visual field using Humphrey perimeter or TAP (Tuebinger automatic perimeter)
 - xii. Optic nerve configuration measured with the HRT-II (Heidelberg Retina Tomograph II)
 - xiii. Retinal nerve fiber layer thickness measured with Stratus OCT
- Collection of intraoperative characteristics or complications from the surgical report

Protocol Version II 5-year CyPass results

- Collection of available postoperative findings and complications
- A written or telephone invitation of the patients to a postoperative examination in the Department of Ophthalmology Neubrandenburg to collect the current, long-term postoperative findings
- The following examinations are performed during the study visit 5 years postoperatively:
 - i. Ophthalmic history
 - ii. Best corrected visual acuity
 - iii. Topical and possibly systemic glaucoma therapy
 - iv. Intraocular pressure using Goldmann tonometer
 - v. Central corneal thickness and the pachymetric correction factor measured with the ultrasonic pachymeter or with the Visante-OCT
 - vi. Visual field using Humphrey perimeter
 - vii. Gonioscopic findings
 - viii. The lens condition or opacities of the natural lens or of the implanted intraocular lens
 - ix. Optic nerve configuration measured with the HRT-II (Heidelberg Retina Tomograph II)
 - x. Nerve fiber thickness measured with Stratus OCT

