3. OBSERVATION PERIOD

All patients potentially taking part in the study were treated with a CyPass micro-stent at the Department of Ophthalmology in Neubrandenburg between 2009 and 2014. Thus, we know the exact date of operation.

The duration of the observation period for each patient depends on the duration of the postoperative period up to the last follow-up visit in the Department of Ophthalmology Neubrandenburg in the context of the study. With follow-up visits, scheduled for the second half of 2016, we expect an average follow-up of more than five years.

4. Procedure

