4.5 Postoperative data collection

We collect the following data prospectively (at the five-year follow-up visit):

- i. *Intermediate history:* First, asking the patients about the postoperative course and the regular check-ups at the registered ophthalmologist. If available, taking the intermediate eye pressure values and the course of the topical therapy, which may have been documented by the Glaucoma pass. Documentation of events such as bleeding or acute IOP-increase. Also documentation of intermediate treatments with date, if any, such as laser treatments.

ii. *Intraocular pressure:* Measuring the intraocular pressure twice in a row using a properly calibrated Goldmann tonometer (Carl Zeiss Meditec, Jena, Germany). The measurements should take place at the same time (± 1 hour) as preoperatively. Documentation of the average value of both measurements is required. If there is a difference of more than three mmHg between these two measurements, a third measurement is taken and the average of all three measurements is documented. The physician doctor measure the intraocular pressure and the assistant reads it. The target pressure is determined according to the criteria of WGA (World Glaucoma Association) [7]. We initially classify the patients into three groups according to visual field damage (mean deviation):

- mild damage (> -5 dB to -10 dB): target IOP ≤ 21 mmHg and IOP reduction $\geq 20\%$
- moderate damage (> -10 dB to -15 dB): target IOP ≤ 18 mmHg and IOP reduction $\geq 30\%$
- severe damage (> -15 dB): target IOP ≤ 15 mmHg and IOP reduction $\geq 40\%$

iii. *Central corneal thickness:* A corneal topography is performed using Visante OCT (Model: 1000, Carl Zeiss Meditec, Jena, Germany). We define the thinnest part of the cornea as central corneal thickness. Alternatively, if the Visante OCT topography is not available (e.g., blepharospasm), three measurements are taken by means of an ultrasonic pachymeter (OcuScan, Alcon, Fort Worth, Texas, USA) to determine the central corneal thickness. The average of these three measurements is considered central corneal thickness.

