iv. *Visual field:* The visual field examination is performed by using the Humphrey Perimeter (Humphrey Field Analyzer, Model 720i, Carl Zeiss Meditec, Jena, Germany) with threshold test centrally 24-2. The visual field is evaluated with the help of the MD value and the PSD value. The rate of progression is expressed in the form of dB / year [8]. As a significant clinical change (improvement or worsening), MD values of ≥ 3 decibels are assessed [9]. In addition, the visual field defects in the central 5-degree visual field are counted in all four quadrants (4 visual field points in total) and evaluated as follows: points with sensitivity level > 10 dB are classified with 0 point, while the points with ≤ 10 dB are evaluated with 1 point. The points are added and then divided by 4. Thus, in the evaluation, the normal regular central visual field will be rated with 0 and the advanced central scotoma in all four quadrants is rated as 1.0.

v. *Glaucoma therapy:* Number and name of the active ingredients of the prescribed topical and systemic antiglaucomatous medications preoperatively and at follow-up visits are assessed. The duration of the postoperative drug-free phase is documented. The systemic intake of acetazolamide (carbonic anhydrase inhibitor) is documented separately and evaluated as absolute failure.

vi. *Visual acuity:* First, the refraction is measured with an auto refractometer (KR-800S, Topcon, Tokyo, Japan). The best-corrected visual acuity is checked and adjusted with the best possible correction using Snellen chart. For the statistical evaluation, a visual acuity of hand motion is documented as 1/800, light perception as 1/1600, and Nulla-lux as 1/3200 [10].

vii. *The optic disc change:* Pre- and postoperative optic disc measurement is performed using the HRT II (Heidelberg Retina Tomograph II, Heidelberg Engineering GmbH, Heidelberg, Germany). The area of the optic disc and

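### Success and the 3 dB field change are judged at a visit 3 to 8 years after surgery that is labelled five-year, with no analysis that ties either to a defined time

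*Combined protocol and SAP*

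**What the plan says.** Section 2.1.1 of the combined protocol and SAP admits "Patients 3 to 8 years following implantation of a CyPass-Stent between 2009 and 2014". Section 2.3 describes one visit per invited patient: "Inviting patients according to inclusion and exclusion criteria for a single examination and collection of postoperative data after an average of five years". Section 2.4 then gives that visit a fixed time, "The following examinations are performed during the study visit 5 years postoperatively", and section 4.5 does the same: "We collect the following data prospectively (at the five-year follow-up visit". Sections 2.1, 2.3 and 3 treat five years as an average. Section 3 adds that each patient's observation period differs and schedules the visits for the second half of 2016.

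The long-term success rate is a secondary outcome (section 2.1). Section 2.6 defines success by pressure and medication, and complete failure by loss of light perception, systemic carbonic anhydrase inhibitor therapy or second glaucoma surgery. None of these has a time attached. For reoperated eyes, section 2.2 says "We will collect the available data up to the date of the new operation" and classes them as failures. The eligibility limits, including the 3-year minimum, "are considered for the prospective part of the study", so they do not bind eyes taken from records.

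For visual fields, section 4.5 plans a progression rate in dB/year and also a fixed threshold: "As a significant clinical change (improvement or worsening), MD values of ≥ 3 decibels are assessed". Section 3 notes "Thus, we know the exact date of operation", but no stated analysis uses that date. Section 5 names only software and adequate procedures. Its visit-window table has no named column after M36, where the acceptable window is ±181 days.

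**The concern.** Failure by reoperation accumulates with time, and so does a fixed decibel loss in a progressive disease. If each eye is classified once, at whatever time it was seen, the resulting proportion belongs to no particular year. It shifts with the mix of surgery years and cannot be set beside a rate at a stated time from another series.

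The entry rules add an asymmetry. With visits in the second half of 2016, an eye implanted in 2014 that was reoperated early is counted as a failure from the records. A 2014 eye that still functions has generally not reached 3 years and cannot be invited. It counts only if it happens to enter through the records. At stake are a named secondary outcome and the field-worsening part of the main outcome.

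**Working it through.** The plan gives no success rate or progression share to reproduce. Its sample size (84, inflated to 130) concerns a mean difference, and 84 is used below only as a denominator.

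**Inputs from the documents:** implantation 2009 to 2014, visits July to December 2016, eligibility 3 to 8 years, threshold 3 dB, acceptable yearly window ±181 days.

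**Assumptions, none in the documents:** implant and visit dates uniform over those periods, reoperation hazard 5% per year, true field loss 0.5 dB/year, SD of change 2 dB.

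**1. Calendar.**
- An eye implanted on 1 January 2009 has 7.5 to 8.0 years of follow-up at the visit.
- An eye implanted on 1 July 2013 has 3.0 to 3.5 years.
- 2014 implants have 1.5 to just under 3.0 years.
- The share of eyes under 3 years is 1/6 (2014) plus (1/6)(1/4) (part of 2013) = 20.8%.
- Mean follow-up is 4.75 years over all eyes and 5.4 years (SD 1.4) over eyes at 3 years or more. The second figure agrees with the plan's expectation of more than five years.

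**2. Eyes near year 5.** The ±181-day window is 362/365.25 = 0.99 year wide. Over six years of implantation, 0.99/6 = 16.5% of eyes fall in it. Among eyes at 3 years or more the share is 0.165/0.792 = 20.9%, which is about 18 of 84.

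**3. Reoperation.** Cumulative failure is 1 − exp(−0.05t):

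| Follow-up | Failure |
|---|---|
| 3 years | 13.9% |
| 5 years | 22.1% |
| 8 years | 33.0% |
| Averaged over all eyes | 20.8% |
| Averaged over eyes at 3 years or more | 23.4% |

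With a rising hazard (Weibull shape 1.5, 30% failed at 5 years), the two pooled values are 28.2% and 32.7% against 30%.

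**4. Entry asymmetry.** Of the 20.8% of eyes under 3 years, 2.3 points have been reoperated and 18.5 points still function. If none of the functioning ones enters through records, crude failure is 0.208/(1 − 0.185) = 25.6%, against 22.1% at year 5. This is the upper case.

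**5. The 3 dB threshold.** The constant slope that reaches 3 dB is 3/3 = 1.0 dB/year at 3 years, 3/5 = 0.6 at 5 and 3/8 = 0.375 at 8. An eye losing 0.5 dB/year has lost 1.5 dB at 3 years and 4.0 dB at 8. With SD 2 dB, the share worsening by at least 3 dB is 1 − Φ((3 − 0.5t)/2):

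| Follow-up | Share worsening by at least 3 dB |
|---|---|
| 3 years | 22.7% |
| 5 years | 40.1% |
| 8 years | 69.1% |
| Averaged over all eyes | 38.8% |
| Averaged over eyes at 3 years or more | 44.2% |

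**The case against.** The case against has real weight. The plan is open that five years is an average, and the success outcome is called long-term, not five-year. Only the visit labels and the running header say five years. No passage says that success will be pooled into one proportion or that eyes changing by 3 dB will be counted; both are inferred from a silent section 5. The dB/year measure already allows for follow-up length. A single assessment applies only to invited eyes, because records supply month-3, month-6 and unscheduled visits, interim pressures and dated interim treatments. The pooled values also lie close to the year-5 values. All of this stands, and it limits the size of the point. It does not give the success rate a time point or remove the entry asymmetry.

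A reader might infer three stronger things that the documents do not support.

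- **That the pooled rate is badly wrong as a five-year figure.** The average error is about 1 point under a constant hazard, up to about 3 under the rising hazard, and 3 to 4 in the upper case for entry.
- **That a 3 dB count would reflect follow-up length as much as disease.** Follow-up SD of 1.4 to 1.7 years at 0.5 dB/year adds a variance of about 0.47 to 0.76 to a within-time variance of 4, or 11–16% of the total.
- **That the 3-year minimum should be extended to eyes taken from records.** Read as observed follow-up, this would delete every reoperation before year 3. At a 5% yearly hazard, crude failure would fall to about 11%, which inflates success.

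**Conclusion.** The point holds in a limited form. One visit spread over 3 to 8 years is labelled five-year. The success classes and the 3 dB change have no time point, and failures enter at any time while most functioning 2014 implants cannot be invited. The average error in a pooled failure rate is small to modest: 21–23% against 22%, rising to about 26% in the upper case. For the 3 dB share it is 39–44% against 40%. What the pooled figure hides is larger: 14% to 33% failure, and 23% to 69% worsening, between 3 and 8 years. All these sizes rest on assumed uniform dates, hazard, slope and SD. The direction does not: reoperation can only accumulate, and a fixed threshold is easier to reach with longer follow-up in eyes that are progressing. The change is worth making because a named outcome lacks a defined time and the remedy is cheap.

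**What to change.** In section 5:

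1. Estimate freedom from second glaucoma surgery by Kaplan-Meier in all implanted eyes that meet the study population definition. Include eyes under 3 years and deceased patients, censored at last documented follow-up. Report it at 3 and 5 years with 95% CI, and state that it covers only the reoperation component of failure.
2. Report target-IOP success and mean IOP at the visit from a model with years since surgery as covariate, evaluated at 5 years, and give the distribution of follow-up. Use yearly ±181-day windows for description only. With about 18 eyes and 60% success (assumed), the 95% half-width is 1.96√(0.6 × 0.4/18) = 23 points, against 10 points with 84 eyes.
3. Make dB/year the main field measure and show any 3 dB count by year of follow-up.
4. Describe pooled results as 3 to 8 years, average about five, and align the visit labels in sections 2.4 and 4.5.

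The cost is revised wording and a little more analysis. Operation dates are known and records run to the date of reoperation, so no new data are needed. The downside is wider intervals at the yearly points.

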2.1.2 Exclusion criteria

- Patients who live far away or with limited health conditions, to whom the trip to Neubrandenburg cannot reasonably be expected.
- Patients who moved to an unknown address.
- Deceased patients (with evaluation of the existing data).
- Patients who are not interested in participating in the study.

2.3 Study design

Monocentric study with two parts:

- Retrospective part: Collection of preoperative, intraoperative and postoperative data from the medical records
- Prospective part: Inviting patients according to inclusion and exclusion criteria for a single examination and collection of postoperative data after an average of five years

2.4 Study investigation plan

The pre- and intraoperative data, the data of the routine follow-up after 3 and 6 months postoperatively, as well as data of unscheduled examinations are taken retrospectively from the patient files.

- Collection of preoperative findings from the medical record:
 - i. Patient name, date of birth, gender, operated eye and surgery date
 - ii. General diseases and medications
 - iii. Eye diseases and already performed eye operations, if any
 - iv. Best corrected visual acuity
 - v. Topical and systemic glaucoma therapy and duration of glaucoma therapy
 - vi. Time of diagnosis of glaucoma, if available
 - vii. Intraocular pressure using Goldmann tonometer and time of measurement
 - viii. Central corneal thickness and pachymetric correction factor measured with the ultrasonic pachymeter or with Visante-OCT.
 - ix. Classification of the chamber angle width according to Shaffer classification
 - x. The lens condition or existing opacities of the natural lens or presence of an implanted intraocular lens at the time of surgery
 - xi. Visual field using Humphrey perimeter or TAP (Tuebinger automatic perimeter)
 - xii. Optic nerve configuration measured with the HRT-II (Heidelberg Retina Tomograph II)
 - xiii. Retinal nerve fiber layer thickness measured with Stratus OCT
- Collection of intraoperative characteristics or complications from the surgical report

Protocol Version II 5-year CyPass results

- Collection of available postoperative findings and complications
- A written or telephone invitation of the patients to a postoperative examination in the Department of Ophthalmology Neubrandenburg to collect the current, long-term postoperative findings
- The following examinations are performed during the study visit 5 years postoperatively:
 - i. Ophthalmic history
 - ii. Best corrected visual acuity
 - iii. Topical and possibly systemic glaucoma therapy
 - iv. Intraocular pressure using Goldmann tonometer
 - v. Central corneal thickness and the pachymetric correction factor measured with the ultrasonic pachymeter or with the Visante-OCT
 - vi. Visual field using Humphrey perimeter
 - vii. Gonioscopic findings
 - viii. The lens condition or opacities of the natural lens or of the implanted intraocular lens
 - ix. Optic nerve configuration measured with the HRT-II (Heidelberg Retina Tomograph II)
 - x. Nerve fiber thickness measured with Stratus OCT
 - xi. Imaging and evaluation of the CyPass stent and associated bleb with the help of Visante-OCT/UBM (Ultrasound Biomicroscopy)

2.5 Safety relevant results

- Occurrence of accidents on the way from home to Neubrandenburg or the other way back and adverse events during the examination at the Clinic for Ophthalmology Neubrandenburg

2.6 Success of the treatment

We use two classifications to define treatment success:

- The first classification: dividing patients into 2 groups according to the need for postoperative glaucomatous medication: with and without medication. Then we divide each group into 4 subgroups according to the postoperative intraocular pressure achieved: patients with $IOP > 21\text{mmHg}$, patients with $IOP \leq 21\text{mmHg}$ and $> 18\text{mmHg}$, patients with $IOP \leq 18\text{mmHg}$ and $> 15\text{mmHg}$, and patients with $IOP \leq 15\text{mmHg}$.
- The second classification: definition of the treatment success according to the criteria of WGA (World Glaucoma Association) [4]. Complete success is achieved if the target IOP is reached without additional medication. Achieving the target pressure with additional local therapy is rated as qualified success. The loss of visual acuity to 'nulla lux' because of glaucoma progression, the need for systemic therapy with CAI (carbonic anhydrase inhibitor) to reduce pressure or the need for second glaucoma surgery are classified as complete failures.

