2. SYNOPSIS

2.1 Study objective

We designed this study to assess the long-term outcome after implantation of the supraciliary CyPass microstent beyond two years. The long-term results are of considerable importance for the evaluation and positioning of the CyPass stent procedure in the surgical glaucoma treatment armamentarium. We will collect data of a follow-up period of an average of 5 years.

The main research outcome is the determination of the efficacy of CyPass microstent implantation in reducing the intraocular pressure, the number of necessary antiglaucomatous medications and the progression of glaucoma in terms of visual field worsening and progression of glaucomatous optic disc changes.

Another main outcome is the safety of the procedure based on the intraoperative and postoperative complications.

Secondary outcomes include the development of the stent-associated blebs, the long-term success rate of the CyPass stent, and the clinical identification of stent failures.

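### The success rule in 2.6 has no lower IOP limit, so an eye with pathologically low pressure counts as a success and may not be reported as a harm

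*Combined protocol and SAP*

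**What the plan says.** Section 2.6 gives two classifications.

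The second, attributed to WGA criteria, carries the success labels: "Complete success is achieved if the target IOP is reached without additional medication", and "Achieving the target pressure with additional local therapy is rated as qualified success". Complete failure is limited to three events: loss of all light perception through glaucoma progression, systemic carbonic anhydrase inhibitor treatment to lower pressure, and a second glaucoma operation.

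Section 4.5 ii sets the target by visual field damage:

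- mild: "target IOP ≤ 21 mmHg and IOP reduction" of at least 20%
- moderate: "target IOP ≤ 18 mmHg and IOP reduction" of at least 30%
- severe: "target IOP ≤ 15 mmHg and IOP reduction" of at least 40%

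The first classification separates eyes with and without medication: "Then we divide each group into 4 subgroups according to the postoperative intraocular pressure achieved". Its lowest band is 15 mmHg or less, with no floor.

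On safety, section 2.1 says: "Another main outcome is the safety of the procedure based on the intraoperative and postoperative complications". Section 2.4 provides for collecting postoperative complications but does not list them. Sections 2.5 and 7 confine safety results and adverse events to travel and the study examination.

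**The concern.** According to section 1, the stent works by draining aqueous humor into the suprachoroidal space. Excess drainage is thus the opposite way in which the same mechanism can go wrong. A success rule bounded only from above cannot separate a well-controlled eye from an over-drained one.

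At stake is the long-term success rate, which section 2.1 lists among the secondary outcomes. Reporting of harm is also affected: an eye with very low pressure could be counted as a success and appear nowhere as a complication.

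**Working it through.** **Denominator.** Section 2.7 computes 21 × 8² / 4² = 21 × 64 / 16 = 84, and 84 / 0.65 = 129.2, rounded up to 130. Both figures reproduce. Section 2.7 speaks of patients, whereas section 2.2 gives 84 as the minimum number of eyes to be examined. Success is judged per eye, so 84 eyes is used below.

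**Rule check.** Let B be the preoperative IOP and x the IOP at the assessment. From 4.5 ii, the target is met when x ≤ U and (B − x)/B ≥ r, that is, when x ≤ min(U, (1 − r)B). The documents give no distribution of B, so 18, 24 and 30 mmHg are assumed. The highest pressure that meets the target is:

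| Assumed B (mmHg) | Mild: min(21, 0.8B) | Moderate: min(18, 0.7B) | Severe: min(15, 0.6B) |
|---|---|---|---|
| 18 | 14.4 | 12.6 | 10.8 |
| 24 | 19.2 | 16.8 | 14.4 |
| 30 | 21 | 18 | 15 |

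Every pressure below the tabulated value also meets the target. Illustrative pressures of 2, 4, 5 and 6 mmHg pass in all 3 × 4 × 3 = 36 combinations of baseline, pressure and damage stage. These pressures only test the rule; they are not proposed limits. The result hardly depends on the assumed baselines: at 6 mmHg the strictest reduction (40%) is met whenever B ≥ 6 / 0.6 = 10 mmHg.

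**Failure criteria.** None of the three listed events is triggered by low pressure itself. An unmedicated eye in this range is therefore a complete success unless one of those events happens to occur as well.

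**First classification.** The same eye falls in the band of 15 mmHg or less. No band is labelled success or failure, so nothing is mislabelled, but the eye cannot be told apart from well-controlled ones.

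**Safety side.** No section names or defines low pressure as a complication. The restrictions in 2.5 and 7 would not capture it, and the interim events given as examples in 4.5 i are bleeding and an acute pressure rise.

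**Size.** One eye among 84 is 1/84 = 1.2 percentage points. The documents give no rate of low pressure. For assumed rates, if all such eyes otherwise count as complete successes:

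| Assumed share of 84 eyes | Eyes | Fall in complete-success rate |
|---|---|---|
| 0% | 0 | 0 points |
| 1% | 0.8 (about 1) | 1 point |
| 5% | 4.2 (about 4) | 5 points |
| 10% | 8.4 (about 8) | 10 points |

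**The case against.** The strongest objection is that 2.6 and 4.5 ii both refer to WGA criteria, which may contain a lower limit. That source is not in the documents and cannot be checked. However, the protocol writes out its own operative rule and carries no lower limit over, so an analyst following the text would apply none. If a limit was intended, it needs to be stated.

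The size is also open. What counts is pressure at a late assessment, 3 to 8 years after surgery for invited patients, and not early over-drainage. Eyes with a second glaucoma operation are already failures. Because 84 is a minimum and eyes with existing long-term records are added (section 2.2), 1.2 points per eye is an upper value. All of this stands. It limits the likely effect but does not repair the rule.

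A reader might also infer more than the documents support:

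- **That the two main outcomes contradict each other.** The success rate is a secondary outcome. The main efficacy outcome in 2.1 concerns pressure, number of medications, and visual field and optic disc progression. An eye listed under both efficacy and complications would not in itself be a contradiction.
- **That such an eye is certain to be recorded as a safety event.** Complications are collected under 2.4, so it may be. Nothing in the text ensures it.
- **That the severe-damage group is affected most, because of** "severe damage (> -15 dB): target IOP ≤ 15 mmHg and IOP reduction" **of at least 40%.** The very low pressures tested meet the target in all three groups, and no figure shows them to be more frequent in the severe group.
- **That the first classification also misclassifies.** It only sorts eyes into bands.

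**Conclusion.** The point holds for the WGA-based success definition. As written, an eye with pathologically low IOP at the assessment is a complete success without medication and a qualified success with local therapy, unless a listed failure event also applies. This follows from the rule itself and needs no assumption about frequency.

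The effect on the success rate is unknown. It is at most 1.2 points per eye if at least 84 eyes are assessed, and zero if no such eye exists; the rates of 1 to 10% above are assumptions. The change should be made because the rule gives a wrong class and correcting it costs little, not because a large bias has been shown.

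**What to change.** In 2.6, add one numeric lower IOP limit as a condition of both complete and qualified success. The sponsor chooses the value, since the documents give none, and writes it into the protocol before outcome data are extracted or analysed. The timing matters because part of the outcome data already lies in the medical records, and a limit chosen later could be influenced by them. Then:

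- do not count eyes below the limit as successes;
- split the lowest band of the first classification at the same limit;
- report the success rate with and without the limit;
- count eyes below the limit under postoperative complications, so that the safety outcome in 2.1 includes them.

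A single numeric test avoids conflict between a pressure limit and a separate clinical label. IOP is already measured at the study visit, so no new examination is needed. The cost is a short addition to 2.6, one extra table row, and possibly a slightly lower success rate.
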